12. MEASUREMENT OF EFFECT

12.1 Antitumor Effect – Solid Tumors

For the purposes of this study, patients should be re-evaluated for response every 8 weeks. In addition to a baseline scan, confirmatory scans should also be obtained 8 (not less than 4) weeks following initial documentation of objective response.

Response and progression will be evaluated in this study using the new international criteria proposed by the revised Response Evaluation Criteria in Solid Tumors (RECIST) guideline (version 1.1) [Eur J Ca 45:228-247, 2009]. Changes in the largest diameter (unidimensional measurement) of the tumor lesions and the shortest diameter in the case of malignant lymph nodes are used in the RECIST criteria.

12.1.1 Definitions

Evaluable for toxicity. All patients will be evaluable for toxicity from the time of their first treatment with SGI-110 (guadecitabine) and/or belinostat.

Evaluable for objective response. All patients will be evaluable for objective response from the time of their first treatment with SGI-110 (guadecitabine) and belinostat.

Evaluable Non-Target Disease Response. Patients who have lesions present at baseline that are evaluable but do not meet the definitions of measurable disease, have received at least one cycle of therapy, and have had their disease re-evaluated will be considered evaluable for non-target disease. The response assessment is based on the presence, absence, or unequivocal progression of the lesions.

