Considering there are no FDA-approved treatments for chondrosarcoma (that is, patients will not be heavily pretreated with chemotherapy) and noting that combination studies with hypomethylating agents and HDAC inhibitors have shown favorable tolerability as discussed above, a starting dose of 45 mg/m² appears warranted. To closely monitor for unexpected adverse events, both a safety lead-in and continuous toxicity monitoring rule are applied as further described in Section 9.

Regimen Description				
Agent	Dose	Route	Schedule	Cycle Length
SGI-110 (guadecitabine)	45 mg/m ²	Slow SC injection	Days 1-5	28 days (4 weeks)
Belinostat	1,000 mg/m ²	IV over 30 (±5) min*	Days 1-5	

*May extend belinostat infusion to 3 hours if infusion-related reactions occur.

- SGI-110 (guadecitabine) is administered first, followed by belinostat. Separate SGI-110 (guadecitabine) and belinostat administration by at least 10 minutes but no more than 60 minutes.
- **Patients must receive a prophylactic 5-HT3 receptor antagonist prior to belinostat during the first two cycles of treatment – see Section 6.2.3.1.**
- **Patients must receive prophylactic use of growth factor– see Section 6.2.1.1.**

Patients Receiving Belinostat and ASTX727

Beginning with Amendment 5, subsequent patients enrolled on this study will receive treatment with belinostat and ASTX727. These patients will not receive SGI-110 (guadecitabine).

ASTX727 is an orally available DNMT inhibitor which consists of oral cedazuridine, a cytidine deaminase inhibitor, in combination with oral decitabine. ASTX727 is an oral tablet with a fixed dose combination of cedazuridine 100 mg and decitabine 35 mg. See Section 2.2.3 for additional information on ASTX727. Because ASTX727 has not been studied in combination with an HDAC inhibitor, we will repeat the safety lead-in portion of this study among the first 6 patients to receive belinostat and ASTX727. The safety lead-in and the effects of this change on study design and statistical considerations are further described in Section 9.

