Treatment will be administered on an outpatient basis. Patients will be evaluated in the outpatient clinic by the treating investigator and research team on day 1 of each cycle. Patients need not be evaluated by the investigator on the other treatment days in a cycle unless clinically warranted. The study agents will be administered by qualified nursing staff consistent with institutional guidelines for administration of oral and intravenous oncology agents of these classes.

ASTX727 will be given first orally. At least 30 minutes, but no longer than 60 minutes, after ASTX727 is administered, the belinostat infusion may begin. Treatment will continue until a criterion for removal from the study is met (see Section 6.3 Duration of Therapy).

Regimen Description				
Agent	Dose	Route	Schedule	Cycle Length
ASTX727	1 tablet, which consists of cedazuridine 100 mg / decitabine 35 mg	Orally	Days 1-5	28 days (4 weeks)
Belinostat	1,000 mg/m ²	IV over 30 (±5) min*	Days 1-5	

*May extend belinostat infusion to 3 hours if infusion-related reactions occur.

- ASTX727 is administered first, followed by belinostat. Separate ASTX727 and belinostat administration by at least 30 minutes but no more than 60 minutes. Patients will be instructed to bring ASTX727 to clinic and take the medication in clinic to ensure the timeframe is observed.

- **Patients must receive a prophylactic 5-HT3 receptor antagonist prior to belinostat during the first two cycles of treatment – see Section 6.2.3.1.**
- **Patients must receive prophylactic use of growth factor– see Section 6.2.2.1.**

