9. STATISTICAL CONSIDERATIONS

The proposed study is an open-label, single-arm, Simon 2-stage phase 2 clinical trial. Neither

the combination of belinostat and SGI-110 (guadecitabine) nor the combination of belinostat and ASTX727 have been formally evaluated in a phase 1 dose-finding study and therefore a safety lead-in and continuous safety monitoring rule will be applied to monitor for excessive or unexpected toxicity as described in this section.

There is no approved or accepted standard therapy for CS. Chemotherapy is generally ineffective, and no drug has shown clinical efficacy to date. Conventional CS patients are commonly enrolled on clinical trials in the first-line setting. Although chemotherapy is sometimes employed, efficacy is marginal and toxicity is significant. We expect that many sarcoma oncologists would find a chemotherapy control arm problematic, and this would create a barrier to accrual. For these reasons, a single-arm (non-randomized) design is proposed in this rare disease.

With Amendment 5, the study was modified to substitute ASTX727 for SGI-110 (guadecitabine). These are similar agents with the same mechanism of action. At the time of this modification, 6 patients were enrolled and treated with belinostat and SGI-110 (guadecitabine). We will report safety and efficacy endpoints separately for these 6 patients. These 6 patients will be replaced for the purposes of the original study design. The Simon 2-stage design described below will be conducted among patients treated with belinostat and ASTX727. A new safety lead-in will be performed among the first 6 patients treated with belinostat and ASTX727. The continuous toxicity monitoring rule will also apply. The total sample size for the study will increase from 26 patients to 32 patients, accounting for the 6 patients that will be replaced.

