9.1 Study Design/Endpoints

9.1.1 Primary Endpoint

The primary endpoint for this phase 2 study is the objective response rate. Noting that chemotherapy is associated with objective response rates of 8-12% in conventional chondrosarcoma (Fox *et al.*, 2012; Italiano *et al.*, 2013), and most clinical trials with targeted agents have shown response rates of 0%, we will consider an objective response rate of 8% as reflecting the activity of chemotherapy and an objective response rate of 28% suggesting promising activity warranting further study. A Simon optimal 2 stage design is employed. The design calls for 26 patients. In stage one, 13 patients will be enrolled. If 2 or more responses are observed, the study will proceed to full accrual. If 5 or more responses are seen among the 26 patients, the study treatment is considered promising for further study. This design has 85% power with alpha of 0.054 to test for a response rate of 8% (null hypothesis) *versus* 28% (alternative hypothesis). The probability of early stopping is 72%.

With Amendment 5, the study was modified to substitute AST727 for SGI-110 (guadecitabine). At that time, 6 patients had been enrolled and initiated study treatment. We will report safety and efficacy separately for these 6 patients. We will report the objective response rate, progression-free survival and safety and tolerability for this group of patients. These 6 patients will be replaced. The Simon optimal 2 stage design described above will be applied to patients receiving the belinostat and ASTX727 combination.

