9.3 Safety Lead-In

Recognizing that SGI-110 (guadecitabine) and belinostat have not been formally evaluated together, but that previously completed studies have shown DNA hypomethylating agents and

HDAC inhibitors are generally well tolerated in combination, we will perform a safety lead-in among six patients to confirm safety and tolerability of the proposed dose and schedule.

The safety lead-in will apply to the first six patients treated for two cycles (8 weeks). These patients will undergo safety assessments as specified in the study calendar. The study will not proceed to further accrual until these six patients have completed two cycles or 8 weeks of study treatment; however, patients who end study treatment during this period for reasons other than toxicity, *i.e.*, disease progression, will not be replaced. At that time, the study investigators, CTEP, and the DSMB (if applicable) will review the safety data. If two or more patients in the safety lead-in population experience DLTs as defined in Section 9.2, the study team, CTEP, and the DSMB (if applicable) will consider terminating the study, amending the study to evaluate a lower dose level, and/or further evaluating safety at the current dose level among a limited number of additional patients, and the amended protocol and rationale for modification will be submitted to the CIRB for review. The study team, CTEP, and the DSMB (if applicable) may also take such action if safety concerns exist even in the absence of 2 or more DLTs occurring during the safety lead-in. Formal documentation of the study team's review of toxicity data from the safety lead-in will be provided prior to resuming accrual.

With Amendment 5, the study was modified to substitute AST727 for SGI-110 (guadecitabine). The safety lead-in period will be repeated as described among the first 6 patients treated with ASTX727 and belinostat. However, the safety lead-in period for belinostat and ASTX727 will use a DLT monitoring period of 4 weeks (instead of 8 weeks). The continuous toxicity monitoring rule discussed below will continue to monitor for later-onset toxicity. Definitions of DLT remain the same.

Investigators are expected to report any DLT events directly to the study statistician and the Data Coordinating Center within 24 hours of their knowledge of such an event.

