9.8 Reporting and Exclusions

9.8.1 Evaluation of Toxicity

All patients will be evaluable for toxicity from the time of their first treatment with SGI-110 (guadecitabine) and/or belinostat.

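### Does leftover SGI-110 wording in the evaluability definitions leave the belinostat + ASTX727 Simon test without a defined population?

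*Combined protocol and SAP*

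**What the plan says.** **Evaluability.** Section 12.1.1 on response: "All patients will be evaluable for objective response from the time of their first treatment with SGI-110 (guadecitabine) and belinostat". Section 9.8.1 on toxicity, repeated in 12.1.1: "All patients will be evaluable for toxicity from the time of their first treatment with SGI-110 (guadecitabine) and/or belinostat". Neither names ASTX727.

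**Treatment of the current cohort.** Section 6.1 says of patients enrolled from Amendment 5 onward: "These patients will not receive SGI-110 (guadecitabine". On timing it says: "At least 30 minutes, but no longer than 60 minutes, after ASTX727 is administered, the belinostat infusion may begin".

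**Who is tested.** Section 9: "The Simon 2-stage design described below will be conducted among patients treated with belinostat and ASTX727". Section 9.1.1: "The Simon optimal 2 stage design described above will be applied to patients receiving the belinostat and ASTX727 combination". Section 9.5 adds that the six SGI-110 patients are left out of the Simon count.

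**Response analysis set.** Section 9.8.2 asks for a response category for every patient in the study, ineligible patients included. The main analysis then takes those who met the eligibility criteria, with a possible exception for anyone who took no study drug. Patients who cannot be assessed count as failures. The section names no drug.

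**Replacement.** For the six SGI-110 patients, Section 9 says: "The total sample size for the study will increase from 26 patients to 32 patients, accounting for the 6 patients that will be replaced". For lead-in patients who stop for reasons other than toxicity, Section 9.3 says: "disease progression, will not be replaced". Section 4.4 lets the registration of a never-treated patient be cancelled. Nothing covers a treated ASTX727 patient later found ineligible.

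**The concern.** The response definition joins SGI-110 and belinostat with 'and'. Taken at its word, it fits only the six patients who are outside the primary test and none of the patients inside it. The treatment section, the dose-modification tables, Section 9 and the study calendar were all revised for ASTX727; these two definitions were missed. A primary endpoint whose evaluability text names a drug that the cohort never takes deserves a check.

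Once the drug name is read correctly, a second question appears. Section 12.1.1 would call every treated patient evaluable, while Section 9.8.2 bases conclusions on eligible patients. The decision is a count against fixed cut-offs: at least 2 responses in 13, then at least 5 in 26. If an ineligible patient is dropped and not replaced, the same cut-offs are applied to 12 or 13 patients and then 25. The possible cost is power, together with some freedom to settle the matter after responses are known in an open-label trial.

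**Working it through.** **1. Which text governs the response population?**

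| Question | Where answered | Answer |
|---|---|---|
| Which regimen is tested? | Sections 9, 9.1.1, 9.5 | Belinostat + ASTX727 only |
| Which of those patients enter the main response analysis? | Section 9.8.2 | Eligible patients, possibly excepting the never-treated |
| How is an unassessable patient scored? | Section 9.8.2 | As a failure |
| What does 12.1.1 add? | Section 12.1.1 | A start point for evaluability, with the old drug name |

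The first three rows fix the numerator and denominator of the Simon test without using 12.1.1. An eligible patient who takes ASTX727 and never receives belinostat also has an answer: study drug was taken, so 9.8.2 keeps the patient in, as a failure if not assessed.

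For toxicity, the 'and/or' already covers anyone who starts belinostat. What is literally missed is the 30 to 60 minutes after the first tablet, or a patient who never gets the infusion.

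**2. Reproduce the design.** Inputs from Section 9.1.1: n1 = 13, n = 26, continue with at least 2 responses, succeed with at least 5, p0 = 0.08, p1 = 0.28.

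- Early stopping = (1−p)^13 + 13·p·(1−p)^12. At 8%: 0.3383 + 0.3824 = 0.7206 (stated 72%). At 28%: 0.0140 + 0.0706 = 0.0846.
- P(success) = Σ over x ≥ 2 of Bin(x; 13, p) · P(Y ≥ 5−x), with Y ~ Bin(13, p). At 28%: 0.8512 (stated 85%). At 8%: 0.0453.

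The stated alpha of 0.054 does not reproduce. The exact two-stage value is 0.0453, and ignoring the stage 1 stop gives 0.0523. That is a separate matter, and the true value is the lower one. Correcting the drug name leaves every input above unchanged.

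**3. Treated-but-ineligible patients, not replaced, cut-offs kept.** The documents give no rate; one or two such patients is an assumption.

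| Lost | n1 / n | Power | Type I error |
|---|---|---|---|
| None, or all replaced | 13 / 26 | 0.851 | 0.045 |
| One, stage 2 | 13 / 25 | 0.835 | 0.040 |
| One, stage 1 | 12 / 25 | 0.817 | 0.038 |
| Two, stage 2 | 13 / 24 | 0.815 | 0.035 |
| One in each stage | 12 / 24 | 0.799 | 0.033 |
| Two, stage 1 | 11 / 24 | 0.777 | 0.031 |

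One loss costs 85.1 − 83.5 = 1.6 or 85.1 − 81.7 = 3.4 points of power. Removing a patient can only lower the response count. The chance that the eligible-only and all-treated counts lead to different decisions is therefore this same drop, not an additional effect.

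**4. Can the unstated replacement policy inflate error?** Any go decision reached without a replacement would also be reached after adding one more patient against the same cut-offs. So whether replacement is always, never or sometimes used, the go decisions lie within those of the full 13/26 design. With at most 13 and then 26 eligible patients, type I error stays at or below 0.045.

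**The case for a change.** The strongest reply is that Section 9.8.2 does not cure Section 12.1.1. With the drug name put right, one section counts all treated patients and the other counts eligible ones, and the decision can turn on a single response. If the one ineligible patient is known to have responded, counting or excluding that patient changes the decision with probability 5.8% (stage 2 patient) or 12.1% (stage 1 patient) at a true rate of 28%. These are the power drops divided by 0.28. A sentence on replacement would cost almost nothing.

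Part of this stands: the drug name is wrong, and no sentence settles replacement. But the choice between counting and excluding is not open. Section 9.8.2 says that conclusions rest on eligible patients and that subset analyses cannot support efficacy claims. Being evaluable under 12.1.1 and belonging to the main analysis set under 9.8.2 are different things, and the second decides the test. Only replacement is unsettled. There, a fixed accrual of 13 to 26 and a total of 26 + 6 = 32, with one named replaced group, read most naturally as no further replacement. The 5.8% and 12.1% also presuppose a patient who was treated, found ineligible and responded. Section 4.3.1 has sites confirm all eligibility criteria before registration, which should keep such cases few.

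**Conclusion.** No change to the plan is needed. The SGI-110 wording in 9.8.1 and 12.1.1 is a clerical slip from Amendment 5. The tested cohort is stated in Sections 9, 9.1.1 and 9.5 and the analysis set in 9.8.2, so an analyst would build the right population, and no number depends on the stale name.

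The replacement question is a detail left unstated. Its effect rests on an assumed count of treated-but-ineligible patients: 1.6 to 3.4 points of power for one, and 85.1 − 81.5 = 3.6 to 85.1 − 77.7 = 7.4 points for two. Type I error falls in every case. Replacing instead would hold power at 85.1% but raise accrual above 32 by one per patient, about 0.5 to 1 month each at the planned 1–2 patients per month. Either course is defensible. These figures assume that the cut-offs of 2 and 5 are kept and that the true response rates are those in Section 9.1.1.

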12.1.2 Disease Parameters

Measurable disease. Measurable lesions are defined as those that can be accurately measured in at least one dimension (longest diameter to be recorded) as ≥ 20 mm (≥ 2 cm) by chest x-ray or as ≥ 10 mm (≥ 1 cm) with CT scan, MRI, or calipers by clinical exam. All tumor measurements must be recorded in millimeters (or decimal fractions of centimeters).

Note: Tumor lesions that are situated in a previously irradiated area might or might not be considered measurable.

Malignant lymph nodes. To be considered pathologically enlarged and measurable, a lymph node must be ≥ 15 mm (≥ 1.5 cm) in short axis when assessed by CT scan (CT scan slice thickness recommended to be no greater than 5 mm [0.5 cm]). At baseline and in follow-up, only the short axis will be measured and followed.

Non-measurable disease. All other lesions (or sites of disease), including small lesions (longest diameter < 10 mm [< 1 cm] or pathological lymph nodes with ≥ 10 to < 15 mm [≥ 1 to < 1.5 cm] short axis), are considered non-measurable disease. Bone lesions, leptomeningeal disease,

ascites, pleural/pericardial effusions, lymphangitis cutis/pulmonitis, inflammatory breast disease, and abdominal masses (not followed by CT or MRI), are considered as non-measurable.

Note: Cystic lesions that meet the criteria for radiographically defined simple cysts should not be considered as malignant lesions (neither measurable nor non-measurable) since they are, by definition, simple cysts.

‘Cystic lesions’ thought to represent cystic metastases can be considered as measurable lesions, if they meet the definition of measurability described above. However, if non-cystic lesions are present in the same patient, these are preferred for selection as target lesions.

Target lesions. All measurable lesions up to a maximum of 2 lesions per organ and 5 lesions in total, representative of all involved organs, should be identified as **target lesions** and recorded and measured at baseline. Target lesions should be selected on the basis of their size (lesions with the longest diameter), be representative of all involved organs, but in addition should be those that lend themselves to reproducible repeated measurements. It may be the case that, on occasion, the largest lesion does not lend itself to reproducible measurement in which circumstance the next largest lesion which can be measured reproducibly should be selected. A sum of the diameters (longest for non-nodal lesions, short axis for nodal lesions) for all target lesions will be calculated and reported as the baseline sum diameters. If lymph nodes are to be included in the sum, then only the short axis is added into the sum. The baseline sum diameters will be used as reference to further characterize any objective tumor regression in the measurable dimension of the disease.

Non-target lesions. All other lesions (or sites of disease) including any measurable lesions over and above the 5 target lesions should be identified as **non-target lesions** and should also be recorded at baseline. Measurements of these lesions are not required, but the presence, absence, or in rare cases unequivocal progression of each should be noted throughout follow-up.

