2. BACKGROUND

2.1 Study Disease

CS is a malignant bone tumor characterized by the production of cartilaginous matrix by neoplastic cells. CS accounts for 20-27% of primary malignant bone cancers and is the second most common primary bone tumor after osteosarcoma (Dorfman and Czerniak, 1995). CS most often occurs in the pelvis but can arise in the femur, humerus, ribs and at other sites. Distinct clinical and histologic subtypes have been described which have variable molecular characteristics, biologic behavior, and responsiveness to treatment (Polychronidou *et al.*, 2017). Conventional chondrosarcomas account for 90% of CS and are subdivided into primary (central) chondrosarcomas which form within the medullary cavity and much less common secondary (peripheral) chondrosarcomas which arise from the cartilage cap of pre-existing benign osteochondromas. The remaining 10% of CS are composed of the dedifferentiated, clear cell, and mesenchymal subtypes. Histologic grade is predictive of local recurrence and metastatic spread. Conventional CS are often low or intermediate grade and pursue an indolent course with low metastatic potential; however, a subset are high grade with a poor prognosis (Bovee *et al.*, 2005). Lower grade tumors often recur with higher histological grade and metastatic potential (Gelderblom *et al.*, 2008).

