3. PATIENT SELECTION

3.1 Eligibility Criteria

3.1.1 Patients must have biopsy-proven conventional CS which is:

- either metastatic or locally advanced and unresectable, and
- measurable at study entry according to RECIST version 1.1 criteria, and
- amenable to biopsy with imaging guidance at no or acceptable risk to the patient as defined by institutional guidelines for research-related biopsies or the treating investigator's assessment.

In addition, the following criteria must be met:

- patients must have at least one lesion measurable by RECIST version 1.1 criteria which has not been previously irradiated.
- patients who have histologic evidence of grade 1 chondrosarcoma only must either be

symptomatic from their disease in the opinion of the treating investigator or demonstrate radiographic evidence of disease progression in the 3 months prior to initiation of study treatment.

Note: Pathology review and confirmation of diagnosis will occur at the site enrolling the patient on this study.

- 3.1.2 Patients may have been treated with any number of prior systemic therapies. Because there are no FDA-approved treatments for this disease, patients who have received no prior systemic therapy are also eligible. However, disease must be deemed surgically unresectable.
- 3.1.3 Age ≥ 18 years. Chondrosarcoma is rarely encountered in children and adolescents.
- 3.1.4 ECOG performance status ≤ 2 (Karnofsky $\geq 60\%$, see Appendix A).
- 3.1.5 Patients must have adequate organ and marrow function as defined below:
 - absolute neutrophil count $\geq 1,000/\text{mm}^3$
 - hemoglobin 8 g/dL
 - platelet count $\geq 75,000/\text{mm}^3$
 - total bilirubin $\leq 1.5 \times$ institutional upper limit of normal (ULN)
 - AST(SGOT)/ALT(SGPT) $\leq 2 \times$ institutional ULN
 - creatinine $\leq 1.5 \times$ institutional ULN
 - OR
 - glomerular filtration rate (GFR*) $\geq 45 \text{ mL/min}/1.73 \text{ m}^2$

*Refer to Appendix B for calculation of GFR
- 3.1.6 Human immunodeficiency virus (HIV)-infected patients on effective anti-retroviral therapy with undetectable viral load within 6 months are eligible for this trial.
- 3.1.7 For patients with evidence of chronic hepatitis B virus (HBV) infection, the HBV viral load must be undetectable on suppressive therapy, if indicated.

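### Section 12.1.2 classes every bone lesion as non-measurable in a trial of a primary bone tumour, so a chondrosarcoma in bone cannot be a target lesion and its shrinkage cannot give a partial response

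*Combined protocol and SAP*

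**What the plan says.** - **Disease.** Section 2.1: "CS is a malignant bone tumor characterized by the production of cartilaginous matrix by neoplastic cells". It adds that conventional tumours are mainly central ones arising in the medullary cavity. Section 3.2.1 excludes the dedifferentiated, mesenchymal and clear cell subtypes.
- **Eligibility.** Section 3.1.1 admits metastatic disease or unresectable locally advanced disease. Either must be "measurable at study entry according to RECIST version 1.1 criteria", and there must be at least one measurable lesion that has not been irradiated.
- **Measurability.** Section 12.1.2 first defines a measurable lesion by size (10 mm or more on CT or MRI). Its list of non-measurable disease then includes "Bone lesions, leptomeningeal disease" and closes with "and abdominal masses (not followed by CT or MRI), are considered as non-measurable". The CT/MRI qualifier follows the abdominal masses entry.
- **Target lesions and response.** Under Section 12.1.2, target lesions are drawn from measurable lesions. Under Section 12.1.4.1, PR is a fall of at least 30% in the sum of target-lesion diameters.
- **Endpoint.** Section 9.1.1: "The primary endpoint for this phase 2 study is the objective response rate". For stage one: "In stage one, 13 patients will be enrolled". "If 2 or more responses are observed, the study will proceed to full accrual". Five or more responses among 26 count as promising.
- **Review.** Section 12.1.7 marks response review as not applicable.

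**The concern.** The list of non-measurable disease looks like general solid-tumour text that was not adapted to a tumour arising in bone; the same list names inflammatory breast disease. Applied literally, it removes the dominant tumour of many locally advanced patients from the only measurement that can yield a PR.

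Two things are at stake. One is who enters: a patient whose sole disease is a large pelvic or femoral primary may be eligible at one centre and ineligible at another. The other is who can be a responder, in a design that decides on 2 of 13 and then 5 of 26 responses. Section 9.5 intends to open the study throughout the ETCTN, so many investigators could be interpreting the rule. The only later confirmation that Section 12.1.4.2 provides concerns progression of non-target lesions, not measurability.

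**Working it through.** **1. What the rules do to a bone primary.**

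| Step | Source | Result for a lesion classed as a bone lesion |
|---|---|---|
| Measurable? | 12.1.2 | No |
| Can be a target lesion? | 12.1.2 | No |
| Its shrinkage can give PR? | 12.1.4.1 | No; PR uses target lesions only |
| Can affect CR? | 12.1.4.2 | Yes; non-target disease must disappear |
| Can affect PD? | 12.1.4.2, 12.1.4.3 | Yes, if progression is unequivocal |
| PR category if it is the only disease? | 12.1.4.3, table for non-measurable disease | None |

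Partial shrinkage of the primary therefore cannot count toward response, while its persistence or growth can count against it.

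**2. A patient with only a bone primary.** There are three possibilities:
- (a) The site applies 12.1.2 strictly. The patient fails 3.1.1 and is not enrolled.
- (b) The site treats the mass as measurable. The patient enrols, the mass is a target lesion and PR is possible, contrary to the wording of 12.1.2.
- (c) The patient is enrolled as measurable but scored under 12.1.2. PR is impossible.

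**3. The plan's own figures.** Inputs from Section 9.1.1: n1 = 13, continue if at least 2 responses; n = 26, promising if at least 5; rates 8% and 28%. With b(x; 13, p) the binomial probability and Y ~ Bin(13, p):

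Power(p) = sum over x = 2 to 13 of b(x; 13, p) × P(Y ≥ 5 − x)

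Stop(p) = (1 − p)^13 + 13p(1 − p)^12

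- Stop(0.08) = 0.721 (stated 72%).
- Power(0.28) = 0.851 (stated 85%).

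Both reproduce. The same formula at 8% gives an alpha of 0.045 against the stated 0.054; that is a separate matter and does not affect this point.

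**4. Effect on power, by possibility.** Under (a) or (b) no enrolled patient is barred from PR by this rule, so the power calculation stays at 0.851. Under (c), let f be the share of enrolled patients who cannot register a response, treating CR in them as nil. The observable rate is then 0.28 × (1 − f). The documents do not give f, so the values below are assumptions.

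| f | Observable rate | Stop at stage 1 | Power |
|---|---|---|---|
| 0 | 0.280 | 0.085 | 0.851 |
| 10% | 0.28 × 0.9 = 0.252 | 0.123 | 0.774 |
| 20% | 0.28 × 0.8 = 0.224 | 0.176 | 0.672 |
| 30% | 0.28 × 0.7 = 0.196 | 0.245 | 0.547 |

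**The case against.** Four arguments can be made against the point.

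- **RECIST 1.1 governs.** Section 3.1.1 sets eligibility by RECIST 1.1 and Section 12.1 cites that guideline for response. Its own rule on bone is not in the documents, the term bone lesion is not defined, and the general size definition in 12.1.2 might be thought sufficient. This stands in part: a reader might infer that locally advanced patients are definitely excluded, and the documents do not establish that. But 12.1.2 is the protocol's own working text and its bone entry is more specific than the size definition. If the cited guideline is more permissive, the protocol conflicts with its reference; if it is not, the eligibility problem remains.
- **The qualifier on CT or MRI might cover the whole list.** It follows abdominal masses, and the punctuation does not carry it back to bone.
- **The power loss needs inconsistent rules.** This stands. The lower power figures require the same patient to be measurable for enrolment and non-measurable for scoring. Section 9.8.2 also bases conclusions on eligible patients, so a patient enrolled in breach of 3.1.1 would fall outside the main analysis. Some exposure remains because Section 12.1.1 treats all treated patients as evaluable for response.
- **The primary tumour still counts.** This stands as a limit. A reader might infer that a bone primary has no bearing on the endpoint, but it matters for CR and PD as non-target disease. A patient with another measurable lesion can be scored PR on that lesion while the bone primary persists without progressing.

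**Conclusion.** The point holds in this form: Section 12.1.2 carries an unqualified rule that keeps a chondrosarcoma in bone out of the target sum, and no other section adapts the rule to this disease. A bone-only patient is either turned away, which narrows the population Section 3.1.1 says it admits, or is measured against the written rule. Sites may choose differently, and no response review is planned that would align them.

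The size cannot be fixed from the documents because the proportion with bone-only disease is not given. A reader might infer that the trial is underpowered. That is not supported: power stays at 85.1% if these patients are screened out, or if the mass is accepted as a target lesion. It falls to 77.4%, 67.2% or 54.7% only if an assumed 10%, 20% or 30% of patients are enrolled, scored under the strict rule, kept in the analysis and have no CR. The firmer consequence is an unclear population and an unclear rule for the sole primary endpoint. This should be corrected, as a clarification.

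**What to change.** Reconcile Sections 3.1.1 and 12.1.2, including the target-lesion paragraph of 12.1.2. Replace the unqualified bone entry with a statement of when a chondrosarcoma lesion arising in bone is measurable on CT or MRI and may be a target lesion, consistent with the RECIST 1.1 criteria the protocol cites. Cross-refer Section 3.1.1 to it. One possible form would treat a bone tumour with a soft-tissue mass of at least 10 mm on CT or MRI as measurable, and other bone lesions as non-target. No section of the protocol uses a soft-tissue component as a criterion, so this is only an example for the sponsor to confirm.

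The drafting cost is one sentence and a cross-reference. CT or MRI every two cycles is already in the study calendar, so no added imaging is needed. The real cost falls on patients already enrolled, if there are any under the current regimen: baseline target-lesion selection on their existing scans may need to be checked against the clarified rule, and the result documented before the response analysis.
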